6.2 General Adverse Event Definitions

Following is a list of general AE definitions. For the purposes of this study, only SAEs occurring within the perioperative period to 90 days postoperative, excluding elective procedures, as well as all AEs related to the operative site should be reported.

Adverse Event

An **AE** is any untoward medical occurrence in a clinical investigation subject, which changes the medical baseline of the subject. An AE can be an unfavorable and unintended sign, symptom or

disease, whether or not related to the study device (AEs may also be referred to as complications). See **Section 6.1**, **Reporting of Adverse Events**, for the AE reporting requirements for this study.

Anticipated Adverse Event

An **anticipated AE** is an AE, of which the nature, severity or degree of incidence is known and identified in applicable product labeling, published literature or the study protocol. The list of anticipated events is provided in **Section 11**, **Risk/Benefit Assessment**.

Serious Adverse Event

A **SAE** meets one or more of the following definitions:

- Led to death
- Led to serious deterioration in the health of the subject, that either resulted in the following:
 - A life-threatening illness or injury
 - A permanent impairment of a body structure or a body function
 - o An in-patient or prolonged hospitalization
 - A medical or surgical intervention to prevent life-threatening illness or injury or permanent impairment to a body structure or a body function
- Led to foetal distress, foetal death or a congenital abnormality or birth defect

Adverse Device Effect

An **adverse device effect** (ADE) is a negative change in the subject's health that may have been caused by, or associated with, the use of the device.

Unanticipated Adverse Device Effect

An **unanticipated adverse device effect** (UADE) is any serious adverse effect on health, safety or any life-threatening problem or death caused by, or associated with, a device if that effect is a problem or death not previously identified in nature, severity or degree of incidence, or any other unanticipated serious problem associated with a device and related to the rights, safety or welfare of subjects.

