Subject demographics and medical histories are collected (age, sex, primary diagnosis, BMI, comorbidities, medications used, smoking history, alcohol use, education level, employment status, confounding orthopedic problems, etc.). 2011 KSS will be presented with respect to improvement from preoperative scores. The Forgotten Joint Score (FJS) will be collected at 2-years **Additional Data** postoperative. Collection Assessment of radiographic outcomes using Anteroposterior (AP). Mediolateral (ML) and Merchant radiographs. A Follow-up Questionnaire is administered to assess patient satisfaction, pain, study device survivorship and capture adverse events (AEs). Collection and evaluation of device related AEs and unanticipated adverse device effects (UADEs). **Primary Objective:** The mean SF-36 physical score at 2-years postoperative will be compared to 47.3 (the reference score from the historical control) with a non-inferiority margin of 2.5 points. • A two sided 90% confidence interval will be computed for the mean SF-36 score. If the lower bound is greater than 44.8, the non-inferiority hypothesis holds. Statistical **Secondary Objectives:** The change of EQ-5D from preoperative to postoperative will be Methodology compared using a paired t-test. The mean ROM at 2-years postoperative will be compared to the reference value from the historical control (124 degrees) with an error margin of 5 degrees. A TOST (two one-sided test) will be used to test the difference. A Kaplan-Meier survival curve for all-cause revision/removals will of the Triathlon PSR insert will be displayed at 10-years postoperative. The survival rate will also be presented with a twosided 95% confidence interval. A total of 250 cases (knees) will be enrolled in the study. **Number of Cases** Cases must receive the appropriate study device to count toward enrollment.

Required Components:

• Triathlon PSR Insert (X3 EtO)

Study Device

Compatible Stryker tibial baseplates, femoral components, and patellar components must be used in accordance with the applicable Instructions for Use and Surgical Technique(s). All components must be cemented with respect to the bone.

Additionally, a variety of compatible Triathlon device accessories may be used, as indicated in the surgical protocol.

Inclusions:

- A. Patient has signed an IRB/EC approved; study specific Informed Patient Consent Form.

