6.1 Reporting of Adverse Events

The AE reporting requirements for this study are as follows:

[figure not shown]
- All AEs that meet the definition of serious (see page 22) and occur within the perioperative period (intraoperative to hospital discharge) to 90 days postoperative
- All AEs related to the operative site, regardless of seriousness or time of occurrence

On postoperative functional evaluations, investigators and SCs will be prompted to question subjects as to whether they have seen a doctor for any reason, been hospitalized for any reason or have a current impediment to their function.

For the 6-, 7-, 8-, 9-year intervals, only a Follow-up Questionnaire will be administered. SCs will be responsible for following up with the subjects regarding any questionable responses received on the Follow-up Questionnaire. If it is determined upon this further investigation that a protocoldefined AE has occurred, the SC will be responsible for completing an AE eCRF, submitting the event to Stryker, and reporting the event to the IRB as required.

The following decision tree facilitates identification of AEs for which reporting is required under this study protocol:

Figure 1. Adverse Event Decision Tree

General Physical Examination Findings

At screening for inclusion into the study, any clinically significant abnormality should be recorded as a preexisting condition and reported on the Demographics eCRF. From the time of consent forward, any new clinically significant findings or abnormalities that meet the definition of a protocol defined AE must also be recorded and documented as an AE.

Adverse Event Reporting Period

The study period during which AEs must be reported is normally defined as the period from the initiation of any study procedures to the end of the study treatment follow-up. The start of study procedures is considered to be the point of consent. Any AEs which fit the protocol defined reportable events must be reported from the time of consent until study completion.

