At each contact with the subject the investigator must seek information on AEs by specific questioning and, as appropriate, by examination. Information on protocol defined AEs should be recorded immediately in the source document and also in the appropriate AE module of the eCRF. All clearly related signs, symptoms and abnormal diagnostic procedure results should be recorded in the source document and grouped under one diagnosis, as appropriate. The clinical course of each event should be followed until resolution or until it is determined at the end of the study that the AE will not resolve.

All operative site events occurring at any time as well as all serious adverse events (SAEs) occurring within the perioperative period to 90 days postoperative will be collected and compared to published data. It is expected that the AE rates reported for the Triathlon Total Knee with the Triathlon PSR insert will be comparable to those for historical Triathlon PS cemented constructs.

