6.3 Study Sponsor Notification by Investigator

Of reportable AEs, certain events must be submitted to Stryker within 24 hours for timely notification:

Adverse events that require time sensitive reporting:

An adverse event should be reported to Stryker Clinical Research either by telephone/fax/email within 24 hours of the site becoming aware of the event if any of the following apply:

- The AE occurs intraoperatively or is related to the surgical procedure.
- The AE is considered by the investigator to be device related or if the investigator is uncertain regarding the device related assessment;
- The AE required a reoperation of the study knee or a revision of any study knee components.

At the time of the initial report, the following information should be provided:

Subject number	Whether study treatment was
 A description of the event 	discontinued
Date of onset	 Investigator assessment of the
Current status	association between the event and
	the study treatment

An AE eCRF for an AE meeting the criteria above should be completed within 24 hours of the investigative center's awareness, and the de-identified source documentation should be submitted to Stryker within 24 hours of the investigative center's awareness. These reports will be evaluated by Stryker to determine if a Product Inquiry (PI) is required.

It is recommended that all other reportable AEs are submitted through eCRF entry within 2 weeks.

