8.2.2 Safety Analyses

The frequency and percentage of all protocol-defined adverse events will be tabulated. All protocol-defined adverse events will be tabulated, and a 95% CI will be presented. For details regarding protocol-defined adverse events, see **Section 6.1**.

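### The synopsis promises device-related AEs and UADEs without limit, but the reporting rule does not clearly cover those away from the knee, and the 8.2.2 safety table follows that rule

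*Combined protocol and SAP*

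**What the plan says.** The Study Synopsis, under additional data collection, lists "Collection and evaluation of device related AEs and unanticipated adverse device effects (UADEs" with no restriction on when or where in the body the event occurs.

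Section 6.1 sets out two reportable classes. The first is serious events that "occur within the perioperative period (intraoperative to hospital discharge) to 90 days postoperative". The second is "All AEs related to the operative site, regardless of seriousness or time of occurrence". Later in the same section the collected events are restated as the same two classes: "All operative site events occurring at any time as well as all serious adverse events (SAEs) occurring within the perioperative period", again up to 90 days. Section 6.2 makes the list restrictive: the events to be reported are "only SAEs occurring within the perioperative period to 90 days postoperative, excluding elective procedures, as well as all AEs related to the operative site".

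Section 6.2 also defines an adverse device effect as a harm that "may have been caused by, or associated with, the use of the device", and defines a UADE as a serious device-associated problem not previously identified in nature, severity or incidence. Neither definition carries a time or site limit.

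Section 6.3 opens with "Of reportable AEs, certain events must be submitted to Stryker within 24 hours". One of its triggers is that the investigator considers the event device-related or is unsure. That trigger has no time or site limit and calls for an AE eCRF.

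Section 8.2.2 states "All protocol-defined adverse events will be tabulated, and a 95% CI will be presented". Sections 8.2.1 and 8.2.2 both send the reader to Section 6.1 for what counts as protocol-defined.

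**The concern.** The synopsis and the reporting rule sort events in different ways. The synopsis sorts by relation to the device. The rule sorts by seriousness, time and operative site. An event can be device-related and still belong to neither class of the rule.

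A site that follows Section 6.2 literally has no clear duty to report such an event, and a statistician who follows Section 8.2 would not count it in the safety table. A later statement that few or no UADEs occurred could then partly reflect the collection rule, and a reader of the results could not tell. Two sites could also read Section 6.3 differently and report different sets of events, which would make pooled frequencies hard to interpret.

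**Working it through.** The plan gives no figure to reproduce here. The check sets the sections side by side and adds one division.

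**Step 1: apply the visible rule of Sections 6.1 and 6.2 to a device-related event.**

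| Device-related event | To day 90 | After day 90 |
|---|---|---|
| Operative site, serious | reportable (both classes) | reportable (site class) |
| Operative site, non-serious | reportable (site class) | reportable (site class) |
| Elsewhere, serious | reportable (SAE class) | in neither class |
| Elsewhere, non-serious | in neither class | in neither class |

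Three of the eight cells fall outside the rule, all of them away from the operative site. A UADE is serious by definition, so for UADEs the open cell is the one elsewhere in the body after day 90.

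**Step 2: does Section 6.3 bring those cells back?** The trigger for device-related or uncertain events would do so if read alone. The opening sentence presents the 24-hour events as drawn from AEs already reportable, and the section ends by giving a slower timeline for all other reportable AEs. Both phrases point to a timing rule within the existing classes, but the trigger itself is unrestricted. The text supports either reading.

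**Step 3: what reaches the analysis?** Section 6.4 requires protocol-defined AEs to be recorded. Section 6.1 uses the same term for events found through the questionnaire in years 6 to 9. Section 8.2 tabulates that set and refers to Section 6.1, not 6.3. So an event notified only under a broad reading of Section 6.3 would still lie outside the 8.2.2 table, as far as the visible text of Section 6.1 goes.

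**Step 4: length of the SAE window.** Inputs: 90 days (Sections 6.1 and 6.2) and 10 years of follow-up (Study Synopsis).

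- 10 × 365.25 = 3,652.5 days
- 90 / 3,652.5 = 0.0246, about 2.5%
- Remainder: about 97.5%

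This is a share of calendar time, not of events.

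**The case against.** The strongest reply is that the plan captures more than the two-class rule suggests. The device-related trigger in Section 6.3 is unrestricted and requires an eCRF. Section 6.1 has sites ask about any doctor visit or hospitalization, and information on AEs must be sought at each contact. Late knee events such as loosening, wear and revision are covered at any time. Limited AE collection is also a legitimate choice for a cleared post-market device. All of this stands. It shows that sites may well hear of these events. It does not settle whether they must report them or whether the events are tabulated under Section 8.2.2.

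Some stronger readings go too far:

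- A reader might infer that late device effects away from the knee are never captured. Section 6.3 can be read to capture them, so the text is ambiguous and does not show a certain gap.
- A reader might infer that the plan produces no rate for device-related events or UADEs. The synopsis lists these as additional data. Section 8.1.2 sends additional data to Section 8.4.1, which summarises them by visit with frequency and percentage for categorical variables. What is not specified is a safety tabulation by device relation with a confidence interval.
- A reader might infer that the decision tree omits device-related events. The tree, and a figure just before the bullets in Section 6.1, are not visible in the text reviewed, so this cannot be assumed. If the tree does have such a branch, it conflicts with the restrictive wording of Section 6.2 and the text still needs reconciling.
- Metal sensitivity is a tempting example, but Sections 11.2 and 11.3 list it as a known risk, so it would ordinarily be an anticipated event and is a weak illustration of a UADE.
- A confidence bound for zero UADEs among 250 cases is not a planned output and would ignore attrition (Section 8.4.2 allows 20% loss), so it does not measure the problem.

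**Conclusion.** The concern holds as an unresolved inconsistency between the synopsis, Sections 6.1 and 6.2, and Section 6.3, with a consequence for Section 8.2. A device-related event away from the operative site is not clearly reportable after day 90 if serious, or at any time if non-serious, and would fall outside the 8.2.2 table. Events at the knee are unaffected.

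The period in which serious events away from the site are outside the rule is about 97.5% of follow-up. How many events that involves cannot be estimated, because the documents give no rate for them. The conclusion assumes that the word restricting the classes in Section 6.2 is meant literally and that the figures not shown do not override it. Confidence is moderate for that reason. The correction should be made because it concerns safety reporting and costs little.

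**What to change.** Reconcile the synopsis with Sections 6.1, 6.2 and 6.3, in one of two ways.

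1. If the synopsis states the intent, say in Sections 6.1 and 6.2 that AEs judged device-related or of uncertain relation, and all UADEs, are protocol-defined AEs whatever their time and body site. Carry this into the decision tree if it does not already say so. In Section 8.2.2, tabulate these events by device relation with a 95% CI.
2. If the two-class rule states the intent, narrow the synopsis, make clear that Section 6.3 only sets timing within those classes, and state the limit wherever UADE results are reported.

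The first option costs protocol wording, a few more AE forms over 10 years and one extra table, with no added visits. The second costs wording only, but leaves the study with less to say about device effects away from the knee.

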6.3 Study Sponsor Notification by Investigator

Of reportable AEs, certain events must be submitted to Stryker within 24 hours for timely notification:

Adverse events that require time sensitive reporting:

An adverse event should be reported to Stryker Clinical Research either by telephone/fax/email within 24 hours of the site becoming aware of the event if any of the following apply:

- The AE occurs intraoperatively or is related to the surgical procedure.
- The AE is considered by the investigator to be device related or if the investigator is uncertain regarding the device related assessment;
- The AE required a reoperation of the study knee or a revision of any study knee components.

At the time of the initial report, the following information should be provided:

Subject number	Whether study treatment was
 A description of the event 	discontinued
Date of onset	 Investigator assessment of the
Current status	association between the event and
	the study treatment

An AE eCRF for an AE meeting the criteria above should be completed within 24 hours of the investigative center's awareness, and the de-identified source documentation should be submitted to Stryker within 24 hours of the investigative center's awareness. These reports will be evaluated by Stryker to determine if a Product Inquiry (PI) is required.

It is recommended that all other reportable AEs are submitted through eCRF entry within 2 weeks.

6.3.1 Ethics Committee/Institutional Review Board Notification by Investigator

Reports of AEs (including follow-up information) must be submitted to the EC or IRB according to their specific requirements. Copies of each report and documentation of EC/IRB notification and receipt will be kept with the investigator's study files.

6.3.2 Device Retrieval Process

If the study device is removed for any reason, Stryker may retrieve the Triathlon PSR Insert and/or adjacent tissues for analysis to help characterize potential device-related complications. In the event that the Triathlon PSR Insert is removed from a study subject,

the procedure outlined in the Retrieved Implant Analysis Protocol (**Appendix E**) should be followed, as allowed by the hospital and institution. In addition:

- 1. When revision of a study subject is scheduled, the study coordinator (SC) should contact the Clinical Study Manager (CSM) or other Stryker Clinical Research personnel assigned to the project, as soon as possible.
- 2. Stryker Clinical Research will send a retrieval container to the SC.
- 3. After the device is explanted, the SC or an identified Stryker field representative will retrieve the device and place it in the retrieval container, following the instructions in **Appendix E**.
- 4. The SC, an identified field representative or Stryker Clinical Research will complete a Product Inquiry (PI).
- 5. If not completed by Stryker Clinical Research, the PI should be emailed to Stryker Product Surveillance at [contact], as well as to the Clinical Research email addresses listed on the Sponsor Contact Sheet.
- 6. The PI should be attached to the retrieval container and sent to Product Surveillance. A de-identified operative report should be included, when available.
- 7. Stryker Clinical Research will follow up with Product Surveillance to obtain a Pl number.
- 8. A summary of results will be provided to the investigator upon his/her request.

6.4 Recording of Adverse Events

All protocol defined AEs occurring during the study period must be recorded; this includes events that occur between visit intervals. The clinical course of each event should be followed until resolution or stabilization.

6.5 Medical Monitoring

It is the responsibility of the investigator to oversee the safety of the study at his/her center. This safety monitoring will include careful assessment and appropriate reporting of AEs, as previously noted. Stryker will conduct formal investigations via the Product Surveillance Department of those AEs which are submitted through our PI System.

7 Data Management

7.1 Database

Data will be collected at each center and entered into Stryker's Electronic Data Capture (EDC) system. The system can be accessed remotely by each investigative center and the data entered will be managed by Stryker. Subject data will be processed and monitored according to the protocol schedule by Stryker or Stryker representatives. Draft specifications to support eCRFs and electronic radiographic evaluation forms are provided in **Appendices F and G**, respectively.

7.2 Confidentiality

This study will comply with the 2002 HIPAA privacy rule. As such, Stryker will only collect that information which is necessary to support the objectives of the clinical study. Stryker will take precautions to ensure that data received is as de-identified as possible. In the case that some identified information is received, Stryker will ensure that any identifying information is not reported. Study subjects will authorize Stryker to use their health information in support of the clinical study during the informed consent process. Should a subject choose to withdraw authorization, Stryker may use data collected prior to the withdrawal of authorization.

7.3 Source Documents

Source data include all information, original records of clinical findings, observations or other activities in a clinical study necessary for evaluation of the study. Source data are contained in source documents. Examples of these original documents and data records include: hospital records, clinical and office charts, study worksheets, laboratory notes, memoranda, subject questionnaires, pharmacy dispensing records, recorded data from automated instruments, radiographs, subject files, and records kept at the pharmacy, at the laboratories and at medicotechnical departments involved in the clinical study.

All data points collected during preoperative and follow-up visits must be documented in the subject's chart. This includes range of motion values, pain and function as well as AEs and additional comments. The informed consent process should also be documented in the patient chart. Monitors, defined further in **Section 9**, will be comparing the eCRFs against source documents for accuracy. The monitors will seek to draw a reference between each data point on the eCRF and the subject's chart. Thus, one cannot derive pain, ROM or function based on a chart note that reads "Patient doing well." Every effort should be made to ensure complete source documentation.

Centers are required to create a source documentation plan including any applicable source documentation worksheets prior to enrollment.

